7.9.2. Analysis of Additional Efficacy Outcomes (Placebo-Controlled Period)

7.9.2.1. MMRM Analysis of Additional Clinical Outcomes

Similar to the primary analysis, the following efficacy outcomes will be assessed using an MMRM analysis: MMSE, ADCS-ADL Prevention Questionnaire, CDR-SB, CFI, and C3. For each efficacy measure, the change from baseline score at each scheduled postbaseline visit (according to the Study Schedule) during the treatment period will be analyzed using MMRM. Also similar to the primary analysis, all data from all participants regardless of dose increase will

be included for the solanezumab and placebo groups. Change from baseline at each visit when the scale/measure is scheduled will be the dependent variable. Visit will be treated as a categorical variable with values equal to the visit numbers at which the composite measure was scheduled. We will assume an unstructured covariance structure. The model for the fixed effects will include the following terms: (i) baseline score for scale/measure, (ii) treatment, (iii) visit, (iv) treatment-by-visit interaction, (v) age, (vi) education, (vii) APOE4 Carrier Status (yes/no), and (viii) baseline florbetapir cortical SUVr.

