The change from baseline score at each visit when the composite score is assessed will be the dependent variable. Visit will be considered a categorical variable with values equal to the visit numbers at which the measure was scheduled. The null hypothesis is that the treatment difference between the solanezumab group versus placebo at Week 240 equals zero.

Secondary and Exploratory Endpoints: Change from baseline will be assessed using NCS analyses for the MMSE, CFI, ADCS-ADL Prevention Questionnaire, CDR-SB, and C3. Analysis will also be done on the RUI-B which will be used to assess health care resource utilization over the course of the study. If a gatekeeping strategy is used for hypothesis testing involving a subset of efficacy endpoints, this strategy will be prespecified in the statistical analysis plan prior to database lock. Additional subgroup analyses will be performed. Imaging variables including PET amyloid imaging and volumetric and functional MRI will be analyzed using both region of interest methods and whole brain analyses. Analyses of plasma A β and CSF biomarkers will be performed. Additional sensitivity analyses will be performed to explore the effect of increasing the dose from 400 mg to 1600 mg partway through the study. These sensitivity analyses will include analyses conducted on the PACC and other clinical measures after censoring all observations after the study-wide dose increase, and analyses to estimate the potential differences in the treatment effect for the original dose and the higher dose by modeling the effects of a time-varying dose indicator variable.

Randomized/Delayed-Start Analysis: The PACC, MMSE, CDR-SB, C3, CFI, and the ADCS-ADL Prevention Questionnaire will be analyzed to investigate the long-term effect of anti-amyloid treatment on cognitive decline in preclinical AD. If the primary A4 results in the placebo-controlled period are positive, disease-modifying effects will be assessed using a noninferiority hypothesis in an MMRM model, in which the specific hypothesis is that the advantage of solanezumab treatment demonstrated in the placebo-controlled period is sufficiently maintained in the open-label period. This randomized/delayed-start analysis will assess whether solanezumab has a persistent effect on disease course.

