6.2. Secondary Objectives

The secondary objectives of the placebo-controlled period of the study are as follows:

- To test the hypothesis that solanezumab will slow the decline of perceived cognitive function and performance of everyday activities, as compared with placebo, using an NCS analysis of the Cognitive Function Index (CFI).
- To assess whether decline in activities of daily living begins by the end of the treatment period, and if so, whether an effect of solanezumab, compared with placebo, can be detected using an NCS analysis of the ADCS-Activities of Daily Living (ADL) Prevention Questionnaire.
- To assess the relationship between treatment effect and time using the PACC.
- To test the hypothesis that solanezumab reduces brain amyloid burden, as compared with placebo, as assessed using florbetapir positron emission tomography (PET) imaging.
- To assess effects of solanezumab on CSF and plasma concentrations of total tau peptides and phosphorylated tau peptides (P-tau).
- To assess effects of solanezumab on CSF concentrations of A β .
- To investigate the effect of treatment with solanezumab on volumetric MRI.
- To assess the safety of solanezumab versus placebo treatment, including AEs and immunogenicity.

The secondary objectives of the open-label period of the study are as follows:

- To assess the persistence of effect of solanezumab treatment in participants with preclinical AD. That is, to test the hypothesis that patients originally randomized to receive placebo and later switched to solanezumab at the start of the open-label period do not “catch up” to patients originally randomized to receive solanezumab in the placebo-controlled period, using a randomized/delayed-start analysis. The main efficacy objective of the

open-label period will be an interim randomized/delayed-start analysis of the PACC.

- To test the hypothesis that solanezumab will continue to slow the decline associated with preclinical AD during open-label treatment, comparing participants initially randomized to solanezumab with participants initially randomized to placebo in the double-blind treatment period, using randomized/delayed-start analysis of the MMSE, CDR-SB, C3, CFI, and the ADCS-ADL Prevention Questionnaire.

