11.2.9. Analysis of Secondary Outcomes (Placebo-Controlled Period)

11.2.9.1. Clinical Outcomes

Similar to the primary analysis, each of the secondary efficacy outcomes will be assessed using an NCS analysis. These secondary efficacy outcomes include MMSE, ADCS-ADL Prevention

Questionnaire, CDR-SB, CFI, and C3. For each secondary efficacy measure, the baseline score and scores at each post-baseline visit during the treatment period will be analyzed using NCS.

Also similar to the primary analysis, all data from all patients regardless of dose increase will be included for the solanezumab and placebo groups.

Each of the secondary efficacy outcomes will be assessed using an MMRM analysis. These secondary efficacy outcomes include MMSE, ADCS-ADL Prevention Questionnaire, CDR-SB, CFI, and C3. For each secondary efficacy measure, scores at each post-baseline visit during the treatment period will be analyzed using MMRM.

An additional MMRM analysis, termed a slopes analysis, will be conducted examining the change from baseline score on the PACC at each scheduled postbaseline visit. The slope analysis will treat time from randomization as a continuous variable.

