5.2. Secondary Objectives

The secondary objectives of the study are as follows:

- To test the hypothesis that solanezumab will slow the decline of perceived cognitive function and performance of everyday activities, as compared with placebo, using NCS analysis of the Cognitive Function Index (CFI).
- To assess whether decline in activities of daily living begins by the end of the treatment period, and if so, whether an effect of solanezumab, compared with placebo, can be detected using NCS analysis of the ADCS-Activities of Daily Living (ADL) Prevention Questionnaire.
- To assess the relationship between treatment effect and time using the PACC.
- To test the hypothesis that solanezumab reduces brain amyloid burden, as compared with placebo, as assessed using florbetapir positron emission tomography (PET) imaging.
- To assess effects of solanezumab on CSF and plasma concentrations of total tau peptides and phosphorylated tau peptides (p-tau).
- To assess effects of solanezumab on CSF concentrations of A β .
- To investigate the effect of treatment with solanezumab on volumetric MRI.

- To assess the safety of solanezumab versus placebo treatment, including AEs and immunogenicity.

The secondary objectives of the open-label period of the study are as follows:

- To assess the persistence of effect of solanezumab treatment in participants with preclinical AD. That is, to test the hypothesis that participants originally randomized to receive placebo and later switched to solanezumab at the start of the open-label period do not “catch up” to participants originally randomized to receive solanezumab in the placebo-controlled period, using a randomized/delayed-start analysis. The main efficacy objective of the open-label period will be an interim randomized/delayed-start analysis of the PACC at the time of database lock for the placebo-controlled period using data available up to 2 years in the open-label period.
- To test the hypothesis that solanezumab will continue to slow the decline associated with preclinical AD during open-label treatment, comparing participants initially randomized to solanezumab with participants initially randomized to placebo in the placebo-controlled treatment period, using randomized/delayed-start analysis of the MMSE, CDR-SB, C3, CFI, and the ADCS-ADL Prevention Questionnaire.

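### SAP 7.9.2.1 gives CFI, ADCS-ADL and three other scales only a categorical-visit MMRM in the full mITT set, with no contrast time, although the objectives and protocol specify NCS

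*SAP*

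**What the plan says.** **Objectives.** SAP 5.2 and Protocol 6.2 each name NCS as the method for the CFI objective and for the ADCS-ADL objective. For ADCS-ADL, SAP 5.2 asks whether an effect "can be detected using NCS analysis of the ADCS-Activities of Daily Living (ADL) Prevention Questionnaire".

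**Protocol methods.** The Synopsis extends NCS to all five scales: "Change from baseline will be assessed using NCS analyses for the MMSE, CFI, ADCS-ADL Prevention Questionnaire, CDR-SB, and C3". Section 11.2.9.1 agrees: "Similar to the primary analysis, each of the secondary efficacy outcomes will be assessed using an NCS analysis". Two paragraphs later the same section says "Each of the secondary efficacy outcomes will be assessed using an MMRM analysis", lists the same five scales, and does not say which method leads.

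**SAP methods.** Section 7.9.2.1 carries forward only the second of these: "Similar to the primary analysis, the following efficacy outcomes will be assessed using an MMRM analysis: MMSE, ADCS-ADL Prevention Questionnaire, CDR-SB, CFI, and C3". On time it says: "Visit will be treated as a categorical variable with values equal to the visit numbers at which the composite measure was scheduled". It states no null hypothesis and no visit or week for the treatment contrast. The PACC sections do: 7.9.1.1 (NCS) and 7.9.1.2.1 (MMRM) both test at 240 weeks.

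**NCS on these scales elsewhere in the SAP.** It appears in completers (7.9.2.3) and in data censored at the first dose escalation (7.9.1.2.3). SAP 7.11 gives NCS to continuous RUI-B data, which serve an exploratory objective.

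**The concern.** Two things are unsettled for the five scales: which model provides the test, and at what time.

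The model matters because of the hiatus in SAP 6.1. Participants could pause and later resume without a visit counting as missed, so one visit number can cover different elapsed times. An NCS on actual dates handles that; a model with visit as a category does not. The SAP recognises the problem for florbetapir, plasma, vMRI and CSF (7.12) and adds a continuous-time analysis for each. It adds none for these clinical scales in the mITT set.

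The two models also use different data. Under SAP 7.2, continuous-time analyses take every post-baseline observation in the placebo-controlled phase. An MMRM takes only scheduled visits, plus late scores carried back within 8 weeks.

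The time matters because a treatment-by-visit model yields one contrast per visit. With none named, the result to be reported for CFI or ADCS-ADL is not fixed in advance.

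**Working it through.** The plan states no figure on this point, so the main check is a comparison of text. Two small calculations follow.

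**1. Method by section**

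| Place | CFI, ADCS-ADL | MMSE, CDR-SB, C3 | Data |
|---|---|---|---|
| Protocol 6.2, SAP 5.2 | NCS | no method in these objectives | not stated there |
| Protocol Synopsis | NCS | NCS | not restricted to a subset |
| Protocol 11.2.9.1 | NCS, then MMRM | NCS, then MMRM | all data regardless of dose |
| SAP 7.9.2.1 | MMRM only | MMRM only | all data regardless of dose; mITT by SAP 7.5 |
| SAP 7.9.2.3 | NCS | NCS | completers only |
| SAP 7.9.1.2.3 | NCS | NCS | before first escalation only; no specific endpoint |

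The NCS that the objectives call for, on all data in mITT, is absent. The opening words of 7.9.2.1 liken it to the primary analysis. That no longer fits: SAP section 4 records that version 3 changed the primary model from MMRM to NCS.

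**2. Last scheduled assessment**

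Reading the columns of the placebo-controlled schedule in Protocol Attachment 1 (early termination apart), with week = 4 × (visit − 6):

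- PACC, which includes MMSE: last at Visit 66, week 4 × 60 = 240.
- CFI, ADCS-ADL and CDR: Visits 18, 33, 48 and 63, weeks 48, 108, 168 and 228.
- C3: Visits 9 to 63, last at week 4 × 57 = 228.
- RUI-B: last at Visit 66, week 240.

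The gap is 240 − 228 = 12 weeks for four of the five scales. The RUI-B row, in the same table, does reach Visit 66, which supports the column reading. The table was extracted from a PDF, however, so this needs a check against the source schedule. If it is right, an MMRM has no scheduled week-240 level for these four scales. The completer NCS, which takes over the primary model and approach, would be estimating 12 weeks past their last scheduled assessment.

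**3. How far a visit label can drift**

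SAP 6.1 says the hiatus extended the end of the period by up to 9 months. It does not say how many participants paused or for how long, so both are assumed here:

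- *p*, the share paused before Visit 63: 10% to 50%.
- *d*, the pause: 3 to 9 months. Nine months as the ceiling for one participant's visit is inferred.

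In weeks, 9 × 30.44 / 7 = 39.1 and 3 × 30.44 / 7 = 13.0. Mean elapsed time at Visit 63 is 228 + *p* × *d*. The added within-visit SD is *d* × √(*p*(1 − *p*)).

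| *p* | *d* (weeks) | Mean (weeks) | Shift | Added SD (weeks) |
|---|---|---|---|---|
| 0.10 | 13.0 | 229.3 | +0.6% | 3.9 |
| 0.25 | 39.1 | 237.8 | +4.3% | 16.9 |
| 0.50 | 39.1 | 247.6 | +8.6% | 19.6 |

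These figures show how loosely the label fits elapsed time. They are not an estimate of change in the treatment contrast, its standard error or power.

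**The case against.** The best defence is that this is an unwritten paragraph and not a changed method. SAP 5.2 itself commits CFI and ADCS-ADL to NCS, 7.5 sets the mITT population, 7.9.1.1 supplies a model to copy, and 7.9.2.1 never says that it replaces NCS. The rationale in the protocol's amendment summary says that MMRM would serve as sensitivity analysis. That stands as evidence of intent, and it supports the fix. It does not cure the SAP, where the only full-mITT model written out for these scales is the MMRM, with no sensitivity label.

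On the contrast time, SAP 7.9.3.2 defines an end-of-period MMRM effect from data through week 240, and 7.9.3.3 applies this to ADCS-ADL, CDR-SB, C3 and CFI. That is a real pointer, but it sits inside the delayed-start analysis and leaves MMSE out. If the last scheduled assessment of these four scales is week 228, it points to a visit at which they are not scheduled.

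Other points stand in part. The protocol does permit an MMRM, so its presence is not the error; the missing NCS and the missing ranking are. The objectives name NCS only for CFI and ADCS-ADL; for the other three scales it comes from the Synopsis and 11.2.9.1. The completer NCS covers all five on continuous time, but only in a subset selected after randomization. The drift figures rest on assumed inputs, and the top one needs half of all participants to pause for the full 9 months.

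**Conclusion.** The concern holds. The SAP's analysis section conflicts with its own objectives and with the protocol: five scales have MMRM as their only written full-mITT method, and two of them (CFI, ADCS-ADL) are named secondary objectives with NCS stated. The contrast time is not given where the analysis is defined.

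This is a secondary-endpoint matter that should be corrected. The likely effect is small to moderate: a mean label shift at Visit 63 of 0.6% to 8.6% under the assumed pauses. No bias between arms is claimed, the PACC test does not change, and Protocol 11.2.11 plans no formal gatekeeping that would carry an error forward. Confidence in the method conflict is high. The week-228 point depends on confirming the schedule.

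**What to change.** 1. In SAP 7.9.2.1, make an NCS model on actual assessment dates in the mITT set the main analysis of CFI and ADCS-ADL, and of MMSE, CDR-SB and C3 to match the protocol. Use the 7.9.1.1 structure and drop the PACC test-version term where it does not apply.
2. Keep the MMRM, label it a sensitivity analysis, and name the visit that it tests.
3. In Protocol 11.2.9.1, label the MMRM paragraph as sensitivity.
4. Check the source schedule and state the contrast time for each scale, in both 7.9.2.1 and 7.9.2.3. If CFI, ADCS-ADL, CDR and C3 do end at Visit 63, either test at week 228 or say openly that a 240-week estimate goes 12 weeks beyond the last scheduled assessment.

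The cost is SAP wording and a one-paragraph protocol clarification. NCS is already planned for these scales in completers and in pre-escalation data, so the mITT run needs little programming and no new data. The change should be made and dated before any unblinded efficacy analysis.

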7.9.2.2. CDR Global Score

Participants will be classified for clinical worsening based on the CDR Global Score. As all participants begin the trial with a CDR Global Score of 0, clinical worsening will be defined as two consecutive CDR Global Scores above 0, or an endpoint CDR Global Score above 0.

Association between treatment and clinical worsening at any time during the double-blind treatment phase will be tested using Fisher's Exact test.

Time to clinical worsening will be assessed through a Kaplan-Meier analysis. For participants who meet the definition of clinical worsening, time to clinical worsening will be defined as the time from randomization to the first non-zero assessment of the CDR Global Score that contributes to the clinical worsening. Participants who do not meet the definition of clinical worsening will be censored at the time of their last CDR Global Score assessment. Treatments will be compared using the log-rank test.

Additionally, time to clinical worsening will also be measured with a Cox proportional hazards model. Definitions of time to event will be identical to those used for the Kaplan-Meier analyses. Time to clinical worsening will be modelled with fixed effects for baseline PACC score, treatment, age, education, APOE4 Carrier Status (yes/no), and baseline florbetapir cortical SUVr. The coefficient associated with treatment will be tested using the Wald Chi-squared statistic.

For both the Kaplan-Meier and the Cox proportional hazard models, APOE4 Carrier Status (yes/no) will also be investigated for differences in time to clinical worsening.

7.9.2.3. Completer Analysis

Separate NCS analysis of the subset of participants who complete the placebo-controlled period will be done for each of the following:

- PACC
- CFI
- ADL-Prevention Questionnaire
- MMSE
- CDR-SB, and
- C3.

The model and approach will be the same as described above for the primary analysis.

7.9.3. Open-Label Period

7.9.3.1. General Considerations

When change from baseline is assessed, participants will be included in the summary only if both a baseline and a postbaseline measure are available. For efficacy analyses (noninferiority and superiority analyses), the baseline will be the last non-missing observation collected prior to the initiation of treatment in the placebo-controlled period, generally, Visit 6.

7.9.3.2. Delayed-Start Analysis of PACC

The main efficacy analysis of the open-label period is to test for disease progression between treatment groups from the end of the placebo-controlled period at Week 240 to the time point in the open-label study period at Week 336 as assessed by the PACC. Comparisons will be made between participants who started solanezumab at the beginning of the placebo-controlled period (early start) and those who started solanezumab at the beginning of the open-label period (delayed start).

In the following description, the difference between solanezumab and placebo at the end of the placebo-controlled period will be denoted Δ_1 ; the difference between early-start and delayed-start solanezumab at the time point of interest in the open-label period will be denoted Δ_2 . Note that Δ_1 is the effect obtained from the MMRM analysis of the placebo-controlled period. The primary delayed-start efficacy measure will be analyzed using estimates from MMRM models, in which three specific hypotheses are tested:

1. Δ_1 is statistically significantly greater than 0.
2. Δ_2 is statistically significantly greater than 0.
3. 90% one-sided confidence limit of $\Delta_2 - 50\% \Delta_1$ is greater than 0.

The change from baseline (prior to the initiation of treatment in the placebo-controlled period) at each visit during both the placebo-controlled period and the open-label period (at the visits when the PACC is assessed) will be the dependent variable. The model for the fixed effects will include terms for: baseline PACC, treatment, visit, treatment-by-visit interaction, education, APOE4 Carrier Status (yes/no), baseline florbetapir cortical SUV_r, and age at baseline. Visit will be considered a categorical variable with values equal to the visit numbers at which the PACC was assessed. An unstructured covariance matrix will be used to model the within-participant variance–covariance errors. If the unstructured covariance structure matrix results in a lack of convergence, the following tests will be used in sequence:

- heterogeneous Toeplitz covariance structure
- heterogeneous autoregressive order 1 covariance structure
- heterogeneous compound symmetry covariance structure
- compound symmetry covariance structure

The first hypothesis will be tested using an estimate of Δ_1 obtained from an MMRM model fit using data from all randomized participants through week 240 (the end of the placebo-controlled period). The second hypothesis will be tested using an estimate of Δ_2 obtained from an MMRM including data from all randomized participants through week 336 (96 weeks of open-label period).

The noninferiority margin for this hypothesis is specified as 50% of the treatment difference observed at the end of the placebo-controlled period. The hypothesis will be tested by constructing a 90% one-sided confidence interval of the difference in least-squares means at the last visit in the delayed-start period. If the lower limit of the confidence interval rules out the difference which would have been obtained if 50% of the observed difference had been lost, the disease progression for the treatment groups will be considered parallel in the open-label period, suggesting the treatment effect is independent of symptomatic effects and that solanezumab has a persistent effect on disease course.

7.9.3.3. Delayed-Start Analyses of Other Efficacy Scales

Several other efficacy measures (ADCS-ADL Prevention Questionnaire, CDR-SB, C3, and CFI) will be analyzed separately using the delayed-start analysis described in Section 7.9.3.2.

Additionally, the Clinician Diagnostic Impression (CDI) will be summarized with proportion of participants in each of the categories by treatment at visits 66 (OLE week 0), 78 (OLE week 48), 90 (OLE week 96), 102 (OLE week 144), and 114 (OLE week 192).

